## 6 OBJECTIVES AND ENDPOINTS

	Objective	Endpoint	Analysis
Primary	Assess the activity of Sym004 in patients with recurrent glioblastoma that are either non-bevacizumab failures (Cohort 1) or who have previously failed bevacizumab (Cohort 2)	The percentage of subjects who remain alive and progression free at 6 months (PFS6) at each dose level	See Section 13.4
Key Secondary	Determine the safety of Sym004 in recurrent GBM patients	The proportion of patients with grade 3, 4, or 5 treatment-related adverse events at each dose level	See Section 13.5.1
Other Secondary	Estimate response rate (RR) within two cohorts of recurrent GBM patients	Proportion of treated patients with a complete or partial response at each dose level	See Section 13.5.2
Other Secondary	Describe overall survival (OS) within two cohorts of recurrent GBM patients	Median OS at each dose level	See Section 13.5.2
Exploratory	Assess the impact of EGFRvIII expression on efficacy (OS and PFS) of Sym004	Median OS and PFS within subgroups of patients defined by EGFRvIII expression and dose level	See Section 13.6
Exploratory	Describe patient-reported quality of life outcomes (PROs)	Mean change from baseline in each Patient-Reported Outcome (PRO) subscale within each Cohort and dose level	See Section 13.6

## 7 INVESTIGATIONAL PLAN

### 7.1 Study Design

This is a phase 2 study that will accrue patients with WHO grade IV recurrent malignant glioma (glioblastoma or gliosarcoma) in two cohorts to assess the efficacy of Sym004. Cohort 1 will include patients who are non-bevacizumab failures; whereas, Cohort 2 will include patients who have progressed after prior treatment with bevacizumab (bevacizumab-failure). Both cohorts will accrue simultaneously, with a goal of 36 subjects in Cohort 1 and 25 subjects in Cohort 2 (see Section 13.8 for justification of sample size). All patients will be treated with Sym004, a recombinant antibody mixture that specifically binds to EGFR. For that reason, only patients whose tumor is determined to be EGFR-amplified will be accrued on this study.

Prior to Amendment 31, approximately 25 subjects received Sym004 at 18 mg/kg intravenously every 2 weeks. After the approval of Amendment 31, subjects who enroll on study will receive 24 mg/kg intravenously every 2 weeks. A maximum of 65 additional subjects (36 in Cohort 1 and 29 in Cohort 2) will be treated at the 24 mg/kg dose level. In addition, subjects who enrolled at the 18 mg/kg dose and who tolerated this dose of Sym004 well (i.e. no skin toxicities  $\geq$  grade 3) will have the option to increase their dose to 24 mg/kg upon approval of Amendment 31. A treatment cycle will be 4 weeks. The patients will have repeat MRIs of the brain every 8 weeks. Subjects with CR, PR, or stable disease may continue on study as long there is no evidence of disease progression or toxicities as described in Section 10.8.1.

The accrual of the first 3-6 patients at the 24 mg/kg dose level, regardless of cohort assignment, will be at a controlled rate for initial safety monitoring. Details concerning this initial accrual at the 24 mg/kg dose level can be found in Section 13.7.4.

For an exploratory objective, we will determine EGFRvIII status at baseline for all patients using archival tumor tissue. If a subject has more than one source of archival or frozen tissue, each source may be requested to determine if EGFRvIII expression has changed over time.

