### 3.2 Design and Procedure

This is a phase 2 study that will accrue patients with WHO grade IV recurrent malignant glioma (glioblastoma or gliosarcoma) in two cohorts to assess the efficacy of Sym004. Cohort 1 will include patients who are non-bevacizumab failures; whereas, Cohort 2 will include patients who have progressed after prior treatment with bevacizumab (bevacizumab-failure). Both cohorts will accrue simultaneously, with 36 subjects in Cohort 1 and 25 subjects in Cohort 2 (see Section 13.8 for justification of sample size). All patients will be treated with Sym004, a recombinant antibody mixture that specifically binds to EGFR. For that reason, only patients whose tumor is determined to be EGFR-amplified (i.e. greater than 15% of cells exhibiting > 5 copies of EGFR loci) will be accrued on this study.

Prior to Amendment 31, approximately 25 subjects received Sym004 at 18 mg/kg intravenously every two weeks. After the approval of Amendment 31, subjects who enroll on study will receive Sym004 at 24 mg/kg intravenously every 2 weeks. A total of 65 additional subjects (36 in Cohort 1 and 29 in Cohort 2) will be treated at the 24 mg/kg dose level. In addition, subjects who enrolled at the 18 mg/kg dose and who tolerated this dose of Sym004 well (i.e. no skin toxicities  $\geq$  grade 3) will have the option to increase their dose to 24 mg/kg upon approval of Amendment 31. A treatment cycle will be 4 weeks. The patients will have repeat MRIs of the brain every 8 weeks.

The accrual of the first 3-6 patients at the 24 mg/kg dose level, regardless of cohort assignment, will be at a controlled rate for initial safety monitoring. Details concerning this initial accrual at the 24 mg/kg dose level can be found in Section 13.7.4.

For an exploratory objective, we will determine EGFRvIII status at baseline for all patients using archival tumor tissue. If a subject has more than one source of archival or frozen tissue, each source may be requested to determine if EGFRvIII expression has changed over time.

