#### 7.1.1 Dose Modification

For subjects receiving 18 mg/kg, the dose of Sym004 may be reduced by up to two dose levels, if the subject experiences grade 3-4 non-hematologic toxicities secondary to Sym004, e.g. skin toxicities, electrolyte disturbances, and gastrointestinal symptoms, or grade 4 neutropenia or thrombocytopenia. Following the initial dose of 18 mg/kg every 2 weeks, if the subject needs to have their dose of Sym004 reduced due to an aforementioned toxicity, then their next dose will be 15 mg/kg every 2 weeks. If another reduction in dose is necessary, the subsequent dose will be 12 mg/kg every 2 weeks. If dose reduction is required more than two times, the patient will be removed from the study.

#### 7.1.2 Dose Modification Post-Amendment 31

For subjects receiving 24 mg/kg, the dose of Sym004 may be reduced by up to two dose levels, if the subject experiences grade 3-4 non-hematologic toxicities secondary to Sym004, e.g. skin toxicities, electrolyte disturbances, and gastrointestinal symptoms, infusion-related reactions, or grade 4 neutropenia or thrombocytopenia. Exceptions to this dose reduction include grade 3 nausea, vomiting, diarrhea or fatigue lasting  $\leq$  5 days with supportive care or grade 3 asymptomatic electrolyte abnormalities. Following the initial dose of 24 mg/kg every 2 weeks, if the subject needs to have their dose of Sym004 reduced due to an aforementioned toxicity, then their next dose will be 18 mg/kg every 2 weeks. If another reduction in dose is necessary, the subsequent dose will be 15 mg/kg every 2 weeks. If dose reduction is required more than two times, the patient will be removed from the study.

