#### 7.1.3 Safety Considerations

According to the Sym004 Investigator's Brochure (v. 8.0, 13-Mar-2017), skin toxicities have been the most frequently reported AEs. To date (20 Jan 2017), approximately 380 subjects with solid tumors, including

subjects with recurrent/metastatic SCCHN, mCRC, ESCC and NSCLC, have been treated with Sym004 in weekly doses of up to 12 mg/kg and in doses every other week of up to 18 mg/kg in ongoing Symphogen-sponsored studies. Anti-EGFR related skin toxicities (including rash, pruritus, skin fissures, dry skin, erythema, and paronychia) have been observed in more than 90% of subjects in the completed and ongoing clinical trials. In subjects who had previously received anti-EGFR mAb therapy, Grade 3 skin toxicities were frequently reported; 50-69% of subjects at a dose of 9 or 12 mg/kg weekly (Sym004-01 Parts B and C and Sym004-02) and 33.3% and 41.2% of subjects at dose levels of 12 mg/kg and 18 mg/kg, respectively, every other week (Sym004-01 Parts D and E).

Other adverse events (AEs) associated with anti-EGFR mAbs, such as electrolyte disturbances (in particular hypomagnesemia), mucositis, and diarrhea were also frequently observed in the completed and ongoing trials. In clinical trials for which AE data are available (Sym004-01-Parts A, B, C, D, E, Sym004-02, and EMR 200637-001-Part A) hypomagnesemia was reported in 54-77% of subjects, and 0-38% of subjects experienced Grade 3 or 4 hypomagnesemia. In the Sym004-01 and Sym004-02 clinical trials, events of hypomagnesemia also represented the majority of serious adverse events (SAEs) that were considered to be related to Sym004 therapy. Serious clinical complications of hypomagnesemia have not been observed. Mucositis was observed in up to 40% of subjects, but the number of subjects experiencing Grade 3 mucositis was low (1 subject). Diarrhea has been reported in up to 59% of subjects; and ≤ 10% of subjects experienced Grade 3 diarrhea. Infusion related reactions have also been observed.

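### The option to escalate from 18 to 24 mg/kg is screened on skin toxicity alone, so a patient who recovered from another severe Sym004-related toxicity still qualifies (minor; at most 2 patients)

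*Combined protocol and SAP*

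**What the plan says.** The escalation option appears twice. Section 3.2 offers it to "subjects who enrolled at the 18 mg/kg dose and who tolerated this dose of Sym004 well (i.e. no skin toxicities" of grade 3 or higher), and Section 7.1 repeats the criterion, for patients "who tolerated this dose of Sym004 well (i.e. no skin toxicities" of grade 3 or higher). No other section adds a condition for taking up the option.

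Several other sections bear on it:

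- **Section 7.1.1** states: "For subjects receiving 18 mg/kg, the dose of Sym004 may be reduced by up to two dose levels". The triggers are related non-hematologic events of grade 3 or 4 (skin, electrolyte and gastrointestinal events are given as examples) and grade 4 neutropenia or thrombocytopenia.
- **Section 7.1.2**, for 24 mg/kg, has similar triggers, names infusion-related reactions, and adds carve-outs: "Exceptions to this dose reduction include grade 3 nausea, vomiting, diarrhea or fatigue lasting" 5 days or less with supportive care, and grade 3 electrolyte abnormalities without symptoms.
- **Section 10.4** holds the next infusion until a related event of grade 3 or higher has come down to grade 2 or lower.
- **Section 7.1** lets patients with response or stable disease stay on study while there is "no evidence of disease progression or toxicities as described in Section 10.8.1". Section 10.8.1 gives the investigator a general power of withdrawal.
- **Section 13.4.2** limits escalation to 2 patients.
- **Section 13.7.4** counts any related grade 3, 4 or 5 event as unacceptable in the early check at 24 mg/kg. It includes escalated patients who are among the first 3 (or 6) to receive that dose.
- **Sections 13.7.2 and 13.8.2** leave escalated patients out of the 24 mg/kg efficacy tests.

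**The concern.** The screen for a higher dose is narrower than the plan's own list of reasons for a lower one. Under 7.1.1, severe electrolyte, gastrointestinal or hematologic toxicity can justify going down from 18 mg/kg. Under 3.2 and 7.1, none of these prevents going up to 24 mg/kg.

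This is a matter of individual safety, not of the trial's inference. The patients concerned would already have had a severe reaction to the drug and would be offered a single dose one third larger. Section 13.7.4 itself describes experience at 24 mg/kg as limited, and Section 7.1.3 describes earlier exposure as "weekly doses of up to 12 mg/kg and in doses every other week of up to 18 mg/kg".

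**Working it through.** The point rests on wording, so the main check sets the sections side by side. The plan states no computed figure to reproduce here.

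**Can a patient with a severe non-skin event reach the option?** Take a patient on 18 mg/kg with a related grade 3 gastrointestinal event.

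1. Section 7.1.1 permits a reduction but does not require one, so the patient can remain on 18 mg/kg.
2. Section 10.4 delays the next infusion until the event is grade 2 or lower. Once it has resolved, dosing resumes, and nothing in 10.4 refers to escalation.
3. Sections 3.2 and 7.1 ask only whether there was skin toxicity of grade 3 or higher. There was none, so the patient qualifies.

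A patient already reduced to 15 or 12 mg/kg is probably not meant to qualify. The criterion refers to tolerating 18 mg/kg, and 13.5.1, 13.7.2 and 13.7.4 all describe a move from 18 to 24 mg/kg. No sentence says so outright, however.

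**How many patients, and how large a step?**

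- Share of the 18 mg/kg group: 2 / 25 = 8% (cap from 13.4.2; about 25 patients from 7.1).
- Share of all patients treated at 24 mg/kg at full accrual: 2 / (36 + 29 + 2) = 2 / 67 = 3.0%.
- Dose step: 24 / 18 = 1.33-fold.
- Two-week total under the earlier weekly regimen: 12 × 2 = 24 mg/kg. The cumulative exposure is therefore not new; the single dose is larger than in the earlier every-other-week regimens.
- Escalated patients in the 24 mg/kg PFS6 tests: 0.

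**Is the case plausible?** The documents give no rate of severe non-skin toxicity among the candidates. As an assumption for scale only, apply the ranges in Section 7.1.3 to 2 independent patients.

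| Event | Rate, p | Expected number of 2 (2p) | Chance of at least one, 1 − (1 − p)² |
|---|---|---|---|
| Grade 3–4 hypomagnesemia, low end | 0 | 0 | 0 |
| Grade 3–4 hypomagnesemia, high end | 0.38 | 0.76 | 1 − 0.62² = 0.62 |
| Grade 3 diarrhea, upper bound | 0.10 | 0.20 | 1 − 0.90² = 0.19 |

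The source for the first two rows is the statement that "0-38% of subjects experienced Grade 3 or 4 hypomagnesemia". These rates come from other tumor types and schedules. They also include events that 7.1.2 would exempt, and Section 7.1.3 adds: "Serious clinical complications of hypomagnesemia have not been observed". They show that the situation can arise, not that it did, and they do not measure what the fix would prevent.

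**Direction of any effect on the 13.7.4 check.** Admitting patients with an earlier severe event would, if anything, make an unacceptable event more likely in the early check, which errs towards caution. Selecting patients without severe skin toxicity could pull the other way, but that comes from the existing skin screen, which should stay.

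**The case against.** The best defense is that the skin criterion is deliberate. Section 7.2 justifies 24 mg/kg by the low rate of severe skin toxicity at 18 mg/kg, so a skin-based screen follows from the rationale. Escalation is an option, not an instruction. A patient kept at 18 mg/kg after a severe non-skin event has already been judged fit for full dose. Section 10.8.1 allows withdrawal for intolerable symptoms or when continuing would be harmful. Section 13.7.4 observes the first 24 mg/kg patient for a full cycle and suspends the study after an unacceptable event. With 16 of the first 19 patients off study for progression before 6 months (7.2), the candidates are few and may have been known to the authors of the amendment, though the documents do not say so.

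Much of this stands as to weight. The rationale explains why skin toxicity is in the criterion. It does not explain why other severe toxicities are absent. Being judged fit to continue at 18 mg/kg is not the same as being fit for a dose one third higher. The withdrawal power concerns staying on study, and the 13.7.4 check acts after exposure; neither is a condition of entry to the higher dose. It is also fair to say that 13.7.4 is a monitoring rule, so its wider definition is not a contradiction. The stronger comparison is with the dose-reduction criteria in 7.1.1 and 7.1.2.

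**Conclusion.** The concern holds, at minor weight. As written, the rule lets a patient who recovered from a severe related non-skin toxicity escalate to 24 mg/kg, provided the patient was not reduced. It reaches at most 2 people, and nothing in the documents shows that either had such an event. The PFS6 tests at 24 mg/kg, the sample size and the stopping rules are untouched. Confidence is high for the textual gap. Its practical consequence cannot be estimated from the documents. The conclusion depends on reading the parenthesis in 3.2 and 7.1 as a definition, which is what its abbreviation means; Section 7.1.1, by contrast, marks its own list as examples.

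**What to change.** In both 3.2 and 7.1, replace the parenthesis with an explicit condition. Escalation is offered only to patients who:

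- are currently receiving 18 mg/kg;
- have had no dose reduction for toxicity;
- have had no skin toxicity of grade 3 or higher; and
- have had no other Sym004-related toxicity that meets the dose-reduction criteria of 7.1.2.

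For patients never reduced, the 7.1.2 exceptions should not bar escalation. Any earlier reduction for toxicity should bar it, whatever the toxicity was.

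The cost is one sentence in each section. One or two patients may lose the option, which could be everyone it covers. The rule is slightly uneven: a patient reduced under 7.1.1, which has no exceptions, for an event that 7.1.2 would now exempt is barred, while a similar patient left at 18 mg/kg is not. That is the price of a simple rule. Sample size, efficacy rules and analyses do not change.

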#### 7.1.1 Dose Modification

For subjects receiving 18 mg/kg, the dose of Sym004 may be reduced by up to two dose levels, if the subject experiences grade 3-4 non-hematologic toxicities secondary to Sym004, e.g. skin toxicities, electrolyte disturbances, and gastrointestinal symptoms, or grade 4 neutropenia or thrombocytopenia. Following the initial dose of 18 mg/kg every 2 weeks, if the subject needs to have their dose of Sym004 reduced due to an aforementioned toxicity, then their next dose will be 15 mg/kg every 2 weeks. If another reduction in dose is necessary, the subsequent dose will be 12 mg/kg every 2 weeks. If dose reduction is required more than two times, the patient will be removed from the study.

#### 7.1.2 Dose Modification Post-Amendment 31

For subjects receiving 24 mg/kg, the dose of Sym004 may be reduced by up to two dose levels, if the subject experiences grade 3-4 non-hematologic toxicities secondary to Sym004, e.g. skin toxicities, electrolyte disturbances, and gastrointestinal symptoms, infusion-related reactions, or grade 4 neutropenia or thrombocytopenia. Exceptions to this dose reduction include grade 3 nausea, vomiting, diarrhea or fatigue lasting  $\leq$  5 days with supportive care or grade 3 asymptomatic electrolyte abnormalities. Following the initial dose of 24 mg/kg every 2 weeks, if the subject needs to have their dose of Sym004 reduced due to an aforementioned toxicity, then their next dose will be 18 mg/kg every 2 weeks. If another reduction in dose is necessary, the subsequent dose will be 15 mg/kg every 2 weeks. If dose reduction is required more than two times, the patient will be removed from the study.

#### 7.1.3 Safety Considerations

According to the Sym004 Investigator's Brochure (v. 8.0, 13-Mar-2017), skin toxicities have been the most frequently reported AEs. To date (20 Jan 2017), approximately 380 subjects with solid tumors, including

subjects with recurrent/metastatic SCCHN, mCRC, ESCC and NSCLC, have been treated with Sym004 in weekly doses of up to 12 mg/kg and in doses every other week of up to 18 mg/kg in ongoing Symphogen-sponsored studies. Anti-EGFR related skin toxicities (including rash, pruritus, skin fissures, dry skin, erythema, and paronychia) have been observed in more than 90% of subjects in the completed and ongoing clinical trials. In subjects who had previously received anti-EGFR mAb therapy, Grade 3 skin toxicities were frequently reported; 50-69% of subjects at a dose of 9 or 12 mg/kg weekly (Sym004-01 Parts B and C and Sym004-02) and 33.3% and 41.2% of subjects at dose levels of 12 mg/kg and 18 mg/kg, respectively, every other week (Sym004-01 Parts D and E).

Other adverse events (AEs) associated with anti-EGFR mAbs, such as electrolyte disturbances (in particular hypomagnesemia), mucositis, and diarrhea were also frequently observed in the completed and ongoing trials. In clinical trials for which AE data are available (Sym004-01-Parts A, B, C, D, E, Sym004-02, and EMR 200637-001-Part A) hypomagnesemia was reported in 54-77% of subjects, and 0-38% of subjects experienced Grade 3 or 4 hypomagnesemia. In the Sym004-01 and Sym004-02 clinical trials, events of hypomagnesemia also represented the majority of serious adverse events (SAEs) that were considered to be related to Sym004 therapy. Serious clinical complications of hypomagnesemia have not been observed. Mucositis was observed in up to 40% of subjects, but the number of subjects experiencing Grade 3 mucositis was low (1 subject). Diarrhea has been reported in up to 59% of subjects; and ≤ 10% of subjects experienced Grade 3 diarrhea. Infusion related reactions have also been observed.

Therefore, subjects will be assessed at each clinic visit, beginning with Cycle 1:Day 15, for skin toxicities according to Duke Medicine's "Guidelines for Management of Cutaneous Toxicity for Patients Receiving Epidermal Growth Factor Receptors" (see Appendix A). Patients will be instructed to call if the rash is painful or interfering with daily functioning. In all ongoing clinical trials, premedication with glucocorticosteroids and antihistamines prior to Sym004 infusion is required. Pre-medications in the current study are described in Section 7.1.5 below. Supplemental guidelines on grading and management of skin toxicities due to Sym004 have been provided by Symphogen in their "Skin Management Booklet." This booklet has been used on other Sym 004 trials and has been provided as a helpful tool for providers.

#### **7.1.4 Delayed Infusions for Scheduling Issues**

A delayed infusion of Sym004, due to scheduling issues, may be re-scheduled within the following 4 days.

#### **7.1.5 Concomitant Medications**

Skin toxicities will be treated according to Duke Medicine's "Guidelines for Management of Cutaneous Toxicity for Patients Receiving Epidermal Growth Factor Receptors" (see Appendix A), in conjunction with Symphogen's "Skin Management Booklet" for Sym004. In the current study, subjects should receive the following premedications, according to institutional guidelines and the judgement of the treating physician: diphenhydramine 50 mg IV and a glucocorticoid steroid, such as hydrocortisone 100 mg IV, 30-60 minutes prior to the first dose. Premedication should be administered for subsequent doses based upon clinical judgment and presence/severity of prior need.

Hypomagnesaemia, mucosal inflammation, and diarrhea will be treated according to institutional guidelines and the treating physician's discretion.

#### **7.1.6 Study Drug Blinding**

Not applicable.

#### **7.1.7 Randomization**

Not applicable.

### 7.1.8 Quality of Life Assessments

Quality of Life will be assessed using standardized and validated questionnaires. These questionnaires include Functional Assessment of Cancer Therapy-Brain (FACT-BR) scale, Functional Assessment of Cancer Therapy-Fatigue (FACT-Fatigue) subscale, version 4, and Beck depression inventory II (BDI-II).

All quality of life assessments will be completed at baseline, prior to the start of every other cycle beginning with Cycle 3, and at the end of the study. These assessments should be completed prior to other study-related evaluations at study visits, if at all possible. If the subject is found to have progressive disease prior to beginning an even-numbered cycle, when HRQoL assessments are not conducted, they may complete these assessments at any time during the clinic visit.

